- A. To determine if HIV is associated with earlier and more significant age-associated changes in FGT by comparing the vaginal microbiome and mucosal inflammation in menopausal WLWH and HIV- menopausal women.
- B. To conduct a pilot randomized clinical trial in menopausal WLWH with symptomatic vaginal atrophy to evaluate the impact of vaginal estradiol treatment on symptoms and biomarkers of FGT aging.

We propose a study nested in the Bronx Women's Interagency HIV Study (WIHS) to compare a phenotype of FGT aging between menopausal WLWH and HIV- women. We will use the following biomarkers of aging: lower levels of lactobacilli (primary outcome), increased dysbiosis, less Ig bacterial coating, and higher levels of mucosal inflammatory mediators. We will also assess bacterial and host cell gene expression using metatranscriptomics (vaginal swabs) and RNAseq (vaginal biopsies). These exploratory "omic" studies may provide insights into the functional significance of observed differences in the composition and Ig coating of vaginal microbiota and their link to vaginal health.

In the first part of the study (Aim 1), 50 HIV+ and 50 HIV- participants aged 45-70 will have 2 study visits one month apart to assess reproducibility of findings. Participants will be frequency matched by age, race and ethnicity into 4 groups: (i) HIV+ aged 45-55; (ii) HIV+ aged 56-70; (iii) HIV- aged 45-55; and (iv) HIV- aged 56-70 years. We have chosen to dichotomize into these age groups based on differences in the taxonomic composition of the microbiome in a recently published study⁴² and potential eligible participants in WIHS. **Figure 1** illustrates the overall study design. Sampling at both study visits will include vaginal swabs for pH, microbiome assessment and evaluation for vaginal infections (candida, bacterial vaginosis [BV], trichomonas), cervicovaginal lavage (CVL) for soluble immune mediators, glycogen, and HIV CVL RNA (shedding), blood for HIV RNA (plasma viral load), CD4 count, estradiol and follicular stimulating hormone (FSH), and vaginal biopsies for exploratory RNAseq (Visit 2 only).

At Visit 2, 50 HIV+ participants with vaginal atrophy will be offered immediate enrollment into a 1:1 randomized trial of vaginal estradiol (n=25) versus no treatment (n=25) to assess whether

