estradiol will improve vaginal symptoms and modify the genital tract aging phenotype. HIV+ women who agree to participate in the trial will have 3 additional study visits: randomization (Visit 3), 6 weeks after randomization (Visit 4) and 12 weeks after randomization (Visit 5). HIV- women can only participate in Aim 1 and will have 2 study visits. HIV+ women can elect to participate in Aim 1 and/or Aim 2 (2 study visits if only Aim 1 is completed; 4 study visits if only Aim 2 is completed; 5 visits if both Aims 1 and 2 are completed).

Inclusion criteria for Aim 1 (first 2 study visits):

- HIV infection or HIV negative
- Females aged 45-70
- Menopause defined by having no menstrual periods for 12 consecutive months, confirmed with serum follicle-stimulating hormone (FSH) level >40 IU/ml and serum estradiol level <20 pg/ml

In the second part of the study (Aim 2), we propose a pilot randomized clinical trial nested in the Bronx WIHS in 50 menopausal WLWH with symptomatic vaginal atrophy to assess the impact of 12 weeks of a topical low-dose estradiol vaginal tablet (Vagifem® 10 µg) on symptoms of atrophy and measures of the vaginal microbiome. Participants will be randomized 1:1 to estradiol (n=25) or no therapy (n=25) and will be followed for 12 weeks. The dosing of Vagifem® will be 1 tablet inserted using a plastic applicator (similar to a tampon) in the vagina daily for 2 weeks followed by 1 tablet inserted twice weekly (i.e., Tuesday and Friday). If we find benefit among women assigned to the estradiol arm, participants randomized to the no therapy arm will be offered vaginal estradiol treatment at the end of the study by their primary care doctor. If participants assigned to Vagifem are symptomatic beyond the 12-week study period and wish to continue Vagifem®, it can be prescribed by their primary care physician. Women will have 3 visits before (Visits 1, 2 and 3) and 2 visits following Vagifem® treatment (Visits 4 and 5). Adherence to Vagifem will be assessed with the use of participant diaries of Vagifem use and counting of used Vagifem applicators.

Inclusion criteria for Aim 2 (randomized clinical trial for HIV+ participants only):

- HIV infection
- Females aged 45-70
- Menopause defined by having no menstrual periods for 12 consecutive months, confirmed with serum follicle-stimulating hormone (FSH) level >40 IU/ml and serum estradiol level <20 pg/ml

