- Symptomatic vaginal atrophy defined as reporting at least once per week in the past 30 days, 1 or more of the following symptoms of moderate or severe intensity:
 - Dryness
 - Itching
 - Irritation
 - Soreness or pain

OR

- Pain associated with sexual activity at least once
- Evidence of atrophy on exam, including thin, pale and dry vaginal and vulvar surfaces
- Agrees not to use vaginal products other than Vagifem during the clinical trial

[figure not shown]
Exclusion criteria for Aims 1 & 2:

- Current unexplained or unevaluated abnormal genital bleeding
- Current or suspected pregnancy
- If < age 55, hysterectomy and has at least one ovary
- Pelvic or vaginal surgery in the 60 days prior to enrollment
- Use of systemic reproductive hormones in the 2 months prior to study enrollment
- Antibiotic use in the past 30 days
- Use of immunosuppressive medications in the prior 60 days including biologics, chemotherapeutics or post-transplant immunosuppressive medications.
- Use of any vaginal or vulvar preparations 1 month prior to enrollment
- Current acute vaginal infection (diagnosed by wet mount at Visit 1 or 2)
- Any serious disease or chronic condition that might interfere with study compliance
- Participants who are unwilling to agree to the provisions of the protocol

Additional Exclusion Criteria for Aim 2 only:

- Current or previous history of breast cancer or estrogen dependent neoplasia
- Known current or past thromboembolic disease (deep vein thrombosis or pulmonary embolism, not including thrombophlebitis), myocardial infarction or stroke
- Known blood clotting disorders including Protein C, Protein S and antithrombin deficiency, Factor V Leiden or prothrombin mutations
- Known severe liver disease including cirrhosis or active Hepatitis B
- History of adverse reaction to vaginal estradiol

Figure 1. Study Design

5. Recruitment

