Women with HIV infection experience menopausal symptoms at an earlier age and are more likely to report symptoms compared to women who do not have HIV. Participants may benefit from study participation because the use of low dose topical estradiol, which has been FDA approved since 2009 for the treatment of vaginal atrophy in menopausal women, may relieve symptoms of vaginal dryness, itching, soreness, pain and urinary symptoms in women with HIV. Participants and others may benefit in the future from information learned from this study. Specifically, if we find that HIV accelerates genital tract aging, this may prompt recommendations for earlier treatment of vaginal atrophy in menopausal women with HIV.

10. Data analysis and sample size:

Aim 1: The primary exposure variables are HIV infection and age. The primary outcome is the vaginal microbiome, specifically the relative abundance and quantities of lactobacillus species as measured by illumina MiSeq and qPCR respectively. Secondary outcomes are relative abundance and quantities of specific BV associated bacteria and quantities of CVL cytokine/chemokines. Exploratory outcomes are quantities and composition of Ig coated bacteria and levels of HIV-1 in the genital tract. Multivariate linear regression will be applied for our analysis. General form of the linear regression model will be: $y_i = \mu + \beta_{age_i} + \gamma_{HIV_i} + \theta_{age_i \times HIV_i} + \delta_i \text{Covariates}_i + \dots + \epsilon_i$, in which y_i is the outcome variables subject to necessary transformation as necessary. Age will be analyzed as a continuous variable to examine the slope or rate of change in lactobacillus and as

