a dichotomous variable (e.g. age 45-55 vs. 56-70) to examine the magnitude of difference between younger and older HIV+ and HIV- menopausal participants. We have chosen the age cut offs above given the significant differences observed in the taxonomic composition of the microbiome in pilot studies when comparing HIV+ menopausal participants in these age ranges and the distribution of eligible participants in WIHS. We will adjust the regression analysis for important covariates including years since menopause, time since HIV diagnosis, HIV plasma viral load, CD4 count, ART use, and HSV-2 serostatus. Both raw p values and the false discovery rate (FDR) according to Benjamini and Hochberg will be examined. To limit the false positive rate in our analysis of secondary outcomes, an arbitrary cutoff of 0.05 for FDR will be used.

Power Considerations: We estimated the power of the proposed study using software PASS (Power and Sample Size Analysis, version 11). Given the sample size of 50 HIV- and 50 HIV+ menopausal participants, we will have >80% power for the minimal detectable difference of 0.6SD and 0.9SD between HIV (or age) group with the significance level of 0.05 and 0.0005 (a conservative Bonferroni correction for 100 independent tests). Data from preliminary studies in our lab investigating the impact of menopause and HIV status on the vaginal microbiome indicated 51 HIV+ menopausal participants had a significantly lower relative abundance of lactobacillus species of 7.3% compared to 23% for 19 HIV- menopausal participants, equivalent to about 0.8SD change. Further when comparing upper and lower age ranges of HIV+ menopausal participants, HIV+ participants age 56-70 (n=28) had significantly lower relative proportions of *L. iners* 7.4% compared to 44.7% in HIV+ menopausal participants aged 47-55.9 (n=23), equivalent to about 1.2SD change. Based on the preliminary data, we are confident that this study will have excellent power to detect effects of age and HIV.

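### Hysterectomy with a retained ovary is excluded only below age 55, so the Aim 1 age groups are selected by different rules and the age contrast may be confounded by surgical history

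*Combined protocol and SAP*

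**What the plan says.** Section 4 (Objectives and Study Design) has a list headed "Exclusion criteria for Aims 1 & 2". One item is "If < age 55, hysterectomy and has at least one ovary". No matching item applies from age 55 upward, and hysterectomy with both ovaries removed is not excluded at any age.

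The same section sets up four groups by HIV status and age (45-55 and 56-70): "Participants will be frequency matched by age, race and ethnicity into 4 groups". Menopause is an entry requirement: "Menopause defined by having no menstrual periods for 12 consecutive months". Blood tests must support this history, and the criterion adds that it is to be "confirmed with serum follicle-stimulating hormone (FSH) level >40 IU/ml and serum estradiol level <20 pg/ml".

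Section 10 (Data analysis and sample size, Aim 1) states: "The primary exposure variables are HIV infection and age". Age is analysed both as a continuous variable and as 45-55 versus 56-70. The regression adjusts for "important covariates including years since menopause, time since HIV diagnosis, HIV plasma viral load, CD4 count, ART use, and HSV-2 serostatus". Hysterectomy and ovarian status are not named.

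Section 1 (Background) predicts that younger HIV+ women will resemble older HIV- women, a comparison that crosses the age groups.

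**The concern.** An eligibility rule that changes with the level of a primary exposure makes the exposure groups differ by construction. Here the change point (55) almost coincides with the group boundary (55/56). The younger group is nearly free of women with a hysterectomy and a retained ovary, and the older group is not. If that history is related to vaginal lactobacilli, part of the younger-versus-older difference reflects surgery rather than age.

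There is a second route through the covariate. After hysterectomy, the absence of periods follows from the operation. FSH and estradiol show that a woman is menopausal now, but not when she became so. If years since menopause were counted from her last period, the count would start at the operation. The error would fall almost entirely in the older group.

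At stake are the Aim 1 age contrast, the age slope, and the predicted similarity of younger HIV+ and older HIV- women. That last comparison is exposed even if hysterectomy is equally common in HIV+ and HIV- women.

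**Working it through.** **The plan's own figure.** Section 10 gives more than 80% power for 0.6 SD at alpha 0.05 and for 0.9 SD at alpha 0.0005, with 50 HIV- and 50 HIV+ women; it applies the same figures to age groups. I assume a two-sided test and 50 v 50 by age. The standard error of the contrast is sqrt(1/50 + 1/50) = 0.20 SD.

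- 0.6 SD, alpha 0.05: 85.1% (normal), 84.4% (t).
- 0.9 SD, alpha 0.0005: 84.6% (normal), 81.1% (t).

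Both stated figures are reproduced.

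**Who can enter.** Hysterectomy with at least one ovary, by age:

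| Age | Rule | Analysis group |
|---|---|---|
| 45-54 | excluded | younger |
| 55 | admitted | younger |
| 56-70 | admitted | older |

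**Route 1: a direct effect of surgical history.** Let q be the share of the older group affected and e the effect on the outcome in SD. If the share in the younger group is taken as 0, the shift in the contrast is q x e. The documents give neither input. I assume q = 10-30% and e = 0.3-0.5 SD.

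| q | e | Shift (SD) | Shift / 0.6 | Shift / SE | Type I error | Power at true 0.6 SD if the shift opposes it |
|---|---|---|---|---|---|---|
| 10% | 0.3 | 0.03 | 5% | 0.15 | 5.3% | 81% |
| 20% | 0.5 | 0.10 | 17% | 0.50 | 7.9% | 70% |
| 30% | 0.5 | 0.15 | 25% | 0.75 | 11.5% | 61% |

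Allowing for 55-year-olds changes little. If ages are spread evenly over the 11 single years 45-55 and the share at age 55 is also q, the younger group's share is q/11. The shift becomes q x e x 10/11, or 0.027-0.136 SD. If e = 0, this route gives no bias.

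**Route 2: mis-dated menopause.** I simulated this with no direct effect of hysterectomy and no age-group effect beyond years since menopause. All inputs are assumptions: natural menopause at mean 49 (SD 3), surgery uniform over ages 35-50, 10-30% of women aged 55 or over affected, and a true slope of -0.03 to -0.05 SD per year since menopause. Dating from last menses overstates years since menopause by about 6.7 years on average in these women. With correct dates the adjusted age-group coefficient is about 0. With surgery-dated values it is -0.03 to -0.12 SD, and the slope for years since menopause shrinks by roughly a sixth to a third. If the true slope is zero, this route also gives no bias.

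**The case against.** The strongest reply is that nothing in the documents shows that harm occurs. No prevalence is given, and no effect of hysterectomy on lactobacilli in women already confirmed as menopausal by FSH and estradiol. Even the assumed shift is at most 0.75 of a standard error. This stands: the claim can only be that the contrast may be biased. A reader might infer that it is biased, and the documents do not support that.

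Four other stronger readings also fail.

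- *That years since menopause cannot be derived.* The plan does not say it is counted from last menses; that is the eligibility definition, not a stated derivation. Section 5 describes a prospective cohort with semiannual visits, and the database extraction list in Table 1 is open-ended, so earlier data might supply an approximate date. What is supported is that no rule is given. Section 5 also allows recruits from outside the cohort, for whom no such history is shown to exist.
- *That women with an unknown date would be dropped.* The plan does not specify complete-case deletion. Its covariate list includes time since HIV diagnosis and plasma viral load, which HIV- women do not have, so it cannot be read that literally. If 5, 10 or 15 of 50 older women were lost, power for 0.6 SD would fall from 84% to 82%, 80% or 77%.
- *That lavage results are distorted because older women may lack a cervix.* Women with both ovaries removed may enter at any age, so women without a uterus can be in either group. Lavage mediators are secondary in Aim 1; the primary outcome is lactobacilli, and Section 6 takes the swabs from the lateral vaginal walls.
- *That the age-by-HIV term is biased.* This needs hysterectomy to differ in frequency by HIV status, which the documents do not address.

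It can also be said that the covariate list is not closed, since it opens with a word meaning that other items may follow. That is true, but nothing commits the analysis to surgical status, or even to recording it from age 55 upward.

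**Conclusion.** The concern holds as a risk of confounding, not as a demonstrated bias. The stated rule makes the two age groups non-comparable on surgical history, with age 55 the only overlap, and neither the matching nor the named covariates correct it. The plan also leaves undefined how years since menopause is obtained in the affected women.

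Size and direction are unknown. Under the assumed 10-30% affected and 0.3-0.5 SD effect, the shift is 0.03-0.15 SD, or 5-25% of the detectable difference. Mis-dating alone could add a spurious age effect of similar size under its own assumptions. Both vanish if the corresponding effect is zero.

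The power statement is correct as written. The randomised Aim 2 comparison is not exposed in this way, because allocation does not depend on age or surgical history. This is a cheap improvement worth making, since the problem cannot be examined later if surgical status was never recorded.

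**What to change.** 1. Record hysterectomy and ovary status for every Aim 1 woman. Applying the exclusion already requires this below 55.
2. Repeat the primary Aim 1 analysis without women who have a hysterectomy and a retained ovary at any age, so that both age groups meet the same rule. Report it beside the main result.
3. In the main model, do not date menopause from last menses in these women. Use earlier cohort data where they give a date. Otherwise set years since menopause to a constant and add an indicator for hysterectomy with a retained ovary, so that the women stay in the analysis. Do not pool them with women who had both ovaries removed, because the dating problem concerns retained ovaries.

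The cost is one history item, about one degree of freedom, and a slightly smaller older group in the sensitivity analysis. Enrolment eligibility is unchanged.

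### Aim 1's only decision cut-off (FDR 0.05) is limited to secondary outcomes, and no threshold or multiplicity rule is set for the primary lactobacillus family

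*Combined protocol and SAP*

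**What the plan says.** All of this is in section 10 (Data analysis and sample size, Aim 1) unless stated otherwise.

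- **Outcome.** The primary outcome is given as "the relative abundance and quantities of lactobacillus species", the first by MiSeq and the second by qPCR. The species are not listed. Section 4 describes the primary outcome only as lower lactobacillus levels.
- **Exposures and model.** "The primary exposure variables are HIV infection and age". The regression formula also contains an age x HIV term.
- **Age.** "Age will be analyzed as a continuous variable to examine the slope or rate of change in lactobacillus", and also as "a dichotomous variable (e.g. age 45-55 vs. 56-70) to examine the magnitude of difference".
- **Error control.** "Both raw p values and the false discovery rate (FDR) according to Benjamini and Hochberg will be examined". The next sentence gives the only cut-off: "To limit the false positive rate in our analysis of secondary outcomes, an arbitrary cutoff of 0.05 for FDR will be used".
- **Power.** With 50 HIV- and 50 HIV+ participants, power is put above 80% for 0.6 SD at level 0.05 and for 0.9 SD at level 0.0005, the latter being a Bonferroni level for 100 tests. Neither level is assigned to a tier of outcomes.

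**The concern.** The plan separates primary, secondary and exploratory outcomes, yet it gives a decision rule only to the second tier. The primary tier has two assays, an open list of species, three model terms and two age codings. Nothing says which result decides the question, or how small a p value must be. As written, the primary claim is less protected than the secondary ones.

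This matters because Aim 1 tests a stated hypothesis. Section 1 predicts that younger women with HIV will resemble older women without it, and section 9 says that a finding of accelerated aging may prompt earlier treatment. One favourable species, term or coding at p<0.05 could be presented as that finding.

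The preliminary data in section 10 show how the choice of measure can move. The HIV comparison uses lactobacillus species overall (7.3% against 23%), while the age comparison uses *L. iners* alone (7.4% against 44.7%).

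**Working it through.** **1. The plan's own power figures.** Two-sample t test, two-sided (sidedness is not stated, so this is an assumption), n = 50 per group, SD = 1. Noncentrality = d x sqrt(n/2) = 5d, with 98 degrees of freedom.

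- d = 0.6, level 0.05: noncentrality 3.0, power 84.4%.
- d = 0.9, level 0.05/100 = 0.0005: noncentrality 4.5, power 81.1%.

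Both exceed 80%, so the stated figures reproduce.

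**2. Size of the primary family.** The documents do not give it. The smallest literal reading is one MiSeq measure and one qPCR measure, three terms (HIV, age, age x HIV) and two age codings: 2 x 3 x 2 = 12 tests. The two study visits, neither of which is named as primary, are not counted.

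**3. Chance of at least one false positive if each test were judged at raw 0.05.** If the tests were independent: 1 - 0.95^12 = 46%. That is too high for this family, because the two age codings overlap and the outcomes may be correlated. It was therefore simulated under the global null, with 25 women per HIV-by-age cell (assumed), ages uniform within each band, normal outcomes and no further covariates. There were 6,000 runs per row.

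| Correlation between the 2 measures | Raw 0.05, any of 12 | Benjamini-Hochberg 0.05 over 12 |
|---|---|---|
| 0 | 33.1% | 4.0% |
| 0.5 | 32.0% | 4.2% |
| 0.8 | 28.6% | 4.4% |

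A repeat with 20,000 runs per row gave 33.4%, 31.4% and 27.3% for raw 0.05, and 4.6%, 4.4% and 4.1% for Benjamini-Hochberg. In round figures, the comparison is 28-33% against 4-5%.

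**4. Sensitivity to the assumed count.** With a single measure (6 tests) the raw figure is 18%. With four measures (24 tests) it is 38-55% over the same correlations. Benjamini-Hochberg stays near 4% in both cases.

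**5. Power under correction.** Benjamini-Hochberg rejects everything that Bonferroni rejects in the same family, so Bonferroni gives a lower bound. At 0.05/12 = 0.00417, for a 50 v 50 comparison:

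- d = 0.6: 53%.
- d = 0.8 (the preliminary HIV difference): noncentrality 4.0, power 85%.

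**The case against.** A reader might infer that every primary test will be done at raw 0.05. The documents do not say so. Raw p values and the FDR are both to be examined, without restriction to a tier. The levels 0.05 and 0.0005 appear only under power, where the second shows that multiplicity was considered. The primary rule could be read as raw 0.05, FDR or 0.0005. The defect is that the rule is undefined, not that a wrong one is set. Examining two quantities does not say which one decides, so this objection corrects the reading but leaves the gap.

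A reader might also count many species and arrive at a much larger error rate. Aim 1 lists no species. The three-species qPCR list belongs to Aim 2, and section 10 itself uses the plural for one aggregate percentage. That is why the two-measure family is the one to lead with.

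The 28-33% also counts more than the harm described. An age effect alone would not show that HIV accelerates aging, and an error in the unpredicted direction would not be reported as support. Take only the HIV and interaction terms, two measures, one coding, independence and the predicted tail (assuming a direction for the interaction too). The chance is then 1 - 0.975^4 = 9.6%, against 2.5% for a single test. The inflation is smaller but remains.

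The two age codings have separate stated purposes, slope and magnitude, so they are not simply repeat attempts. The plan still does not say which one carries the primary conclusion. Finally, Aim 1 is a non-randomised cross-sectional comparison, and its stated implications are hedged, which limits the severity.

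**Conclusion.** The point holds in this form: the only stated decision cut-off in Aim 1 excludes the primary outcome, which is a family with no designated test, threshold or multiplicity rule. If that family were judged on raw p<0.05, which the text permits, the chance of at least one false positive under the global null would be about 28-33%. With Benjamini-Hochberg at 0.05 over the same 12 tests it would be about 4-5%.

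These figures rest on the assumed 12 tests, equal cells, outcome correlations of 0 to 0.8, and no covariates beyond the three terms. They describe the case with no true effects. Where some effects are real, Benjamini-Hochberg limits the expected share of false discoveries rather than the chance of any. This is a cheap improvement, not a fault in the sample size.

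**What to change.** Either of two wording changes in section 10 is enough.

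1. Delete the restriction to secondary outcomes, list the Aim 1 lactobacillus tests (measures, species, terms, age codings), and apply the Benjamini-Hochberg 0.05 cut-off to that list. State whether the list is its own family or pooled with the secondaries; the figures above are for its own.
2. Pre-name one primary measure, age coding and contrast, and place the remaining lactobacillus tests under the cut-off. The contrast must match the claim. An average HIV difference does not test earlier onset, so the age x HIV term is needed if that is the conclusion sought.

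**Cost.** No extra participants or samples are needed. Option 1 loses some power for individual tests, with the Bonferroni lower bounds being 53% for 0.6 SD and 85% for 0.8 SD; the power statement should then be restated at the corrected level. Under option 2, a single HIV contrast at 0.05 keeps the stated power (84% for 0.6 SD). An interaction contrast does not. With 25 per cell its standard error is sqrt(4/25) = 0.4 SD, so a 0.6 SD difference of differences has 32% power, and 80% power needs about 1.13 SD. The plan should say so if that contrast is chosen.

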	Visit 1 Screening	Visit 2 2 nd visit and/or Screening for Trial	Visit 3 Randomized Estradiol vs. No therapy	Visit 4 6 weeks Estradiol vs. No therapy	Visit 5 12 weeks Estradiol vs. No therapy	Safety Call 2, 8, 13 weeks
Eligibility/Informed consent	X	X	X			
Randomization to Estradiol vs. No treatment			X			
WIHS database extraction Demographics, CD4 count, plasma HIV-1 RNA, ART regimen and reported adherence, etc.	X	X				
Vaginal atrophy symptom questionnaire		X	X	X	X	X
Adverse event assessment	X	X	X	X	X	X
Vaginal swabs (n=4-5 per visit) pH, microbiome studies	X	X	X	X	X	
Cervicovaginal lavage (CVL) supernatant Immune mediators, HIV-1 RNA, RSID, saline/KOH, glycogen	X	X	X	X	X	
CVL cell pellet Nugent score, additional microbiome	X	X	X	X	X	
Wet mount (candida, trichomonas, bacterial vaginosis)	X	X				
Vaginal biopsies (2) RNA seq, future immunohistochemistry studies		X			X	
Blood collection Estradiol/FSH levels, HIV-1 RNA, CD4, plasma for future aging biomarkers		X			X	
Clinical Exam to assess for Vaginal Atrophy (VMI)		X			X	

ART=antiretroviral therapy; RSID=rapid semen identification; FSH=follicle stimulating hormone; VMI=vaginal maturation index

7. Potential Risks:

There is a small risk of bruising, blood clots or infection from blood draws. Sometimes the area of needle insertion becomes sore or red. A woman may experience mild discomfort at the time of speculum placement and sample collection. There is a very small risk of injury to the lining of the vagina from the speculum or from the vaginal scraping. There is no discomfort or risk to placement or removal of sterile saline into the vaginal area. There is no risk to CVL or vaginal swab collection. Women may experience a sharp pinch or have pain when vaginal biopsies are performed. In order to minimize the pain and discomfort of the biopsy, we will apply a topical numbing medication (benzocaine gel) to the tissue. There may be stinging, burning, redness, or itching associated with local anesthesia (topical benzocaine gel) which is rare. Biopsies may cause light bleeding. Rarely, a biopsy can cause infection and/or prolonged bleeding. Sometimes a medication is needed to stop the bleeding, which would be applied directly to the

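### Aim 1 samples every woman at two visits to assess reproducibility, but the analysis does not say how the two visits are used; a mixed model on both, with a visit-by-visit report, is a cheap improvement

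*Combined protocol and SAP*

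**What the plan says.** Section 4 (Objectives and Study Design) sets the Aim 1 design: "50 HIV+ and 50 HIV- participants aged 45-70 will have 2 study visits one month apart to assess reproducibility of findings". It adds "Sampling at both study visits will include vaginal swabs for pH, microbiome assessment", and lavage for immune mediators and HIV RNA. Table 1 marks both Visit 1 and Visit 2 for "Vaginal swabs (n=4-5 per visit) pH, microbiome studies" and for "Cervicovaginal lavage (CVL) supernatant Immune mediators, HIV-1 RNA, RSID, saline/KOH, glycogen". Biopsies are at Visit 2 only within Aim 1.

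Section 10, Aim 1, states "Multivariate linear regression will be applied for our analysis". The model has terms for age, HIV, age by HIV and covariates, and one error term. Outcome and error carry the single subscript i, "in which y_i is the outcome variables subject to necessary transformation as necessary". The equation is offered as a general form, and i is not defined as woman or visit. No visit, average of visits or within-woman term appears. The power statement counts 50 and 50 women: "we will have >80% power for the minimal detectable difference of 0.6SD and 0.9SD between HIV (or age) group", at alpha 0.05 and 0.0005 respectively.

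Mixed models are named only under Aim 2. So is the one planned look at variability without intervention, which compares Visit 2 with Visit 3. Section 4 also says "HIV- women can only participate in Aim 1 and will have 2 study visits".

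**The concern.** The second Aim 1 visit has a stated purpose, and Section 10 contains no analysis that serves it: no agreement statistic, no regression repeated at each visit, no visit term. The Aim 2 comparison of Visits 2 and 3 covers only HIV-positive trial participants. Visits 1 and 2 are therefore the only repeat measurement in HIV-negative women, who are half of the Aim 1 comparison.

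Three things are at stake. The reproducibility result may not be produced. Precision that needs no further visit or sample may go unused, mainly for effects smaller than the plan expects and for the age-by-HIV term. And the choice between Visit 1, Visit 2 and a combination is left open until results can be seen.

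**Working it through.** **Inputs.** From Section 10: 50 women per HIV group; 0.6 SD at alpha 0.05; 0.9 SD at alpha 0.0005; a pilot HIV difference of about 0.8 SD. Assumed: two-sided tests; an ICC between Visits 1 and 2 of 0.4 to 0.8, with 0.9 also shown; complete pairs; no covariate adjustment; 25 women in each HIV-by-age cell (cell sizes are not stated). Effects are in single-visit SD.

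**Step 1. Reproduce the plan's figure with one value per woman.** Noncentral t, df = 98, noncentrality d × sqrt(50/2) = 5d.
- d = 0.6, alpha 0.05: noncentrality 3.0, power 84.4%.
- d = 0.9, alpha 0.0005: noncentrality 4.5, power 81.1%.

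Both exceed 80%, as stated. The power statement fits one observation per woman and takes no credit for the second visit. The 80%-power detectable difference at alpha 0.05 is 0.566 SD.

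**Step 2. Effect of using both visits.** With two exchangeable visits, the variance of a woman's mean relative to a single visit is (1 + ICC)/2. Detectable differences are multiplied by its square root.

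| ICC | (1 + ICC)/2 | square root | HIV detectable difference, alpha 0.05 | Power at 0.6 SD |
|---|---|---|---|---|
| one visit | 1 | 1 | 0.566 SD | 84.4% |
| 0.4 | 0.70 | 0.837 | 0.473 SD | 94.4% |
| 0.6 | 0.80 | 0.894 | 0.506 SD | 91.3% |
| 0.8 | 0.90 | 0.949 | 0.537 SD | 87.9% |
| 0.9 | 0.95 | 0.975 | 0.552 SD | 86.2% |

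At the pilot difference of 0.8 SD, power at alpha 0.05 is 97.7% with one visit, and 99.7%, 99.3% and 98.7% with both at ICC 0.4, 0.6 and 0.8. Little can be gained there.

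**Step 3. Age-by-HIV term.** With 25 per cell the SE of the difference of differences is sqrt(4/25) = 0.40 SD, df = 96. The 80%-power detectable difference at alpha 0.05 is 1.132 SD with one visit. With both it is 0.947, 1.012 and 1.074 SD at ICC 0.4, 0.6 and 0.8, and 1.103 SD at 0.9.

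**Step 4. How well the ICC itself would be known.** One-way F interval, two visits per woman.

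| ICC | 95% CI, 100 women | 95% CI, 50 women (one HIV group) |
|---|---|---|
| 0.4 | 0.22 to 0.55 | 0.14 to 0.61 |
| 0.6 | 0.46 to 0.71 | 0.39 to 0.75 |
| 0.8 | 0.72 to 0.86 | 0.67 to 0.88 |

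**The case against.** The strongest reply is that nothing here is wrong. A one-visit regression is valid, the stated power holds, and at 0.8 SD and alpha 0.05 power is already about 98%. The gain rests on an ICC that the documents do not give, and even with both visits only a large age-by-HIV difference is detectable. All of this stands, which is why the point is an improvement and not a defect in the power.

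Four further objections limit what can be claimed.
- That the model takes one outcome per woman is an inference. The equation is a general form with an undefined index. The inference fits the power statement, but the firm finding is only that the use of the two visits is not stated.
- A pooled model with an ICC would not by itself answer the stated purpose. Reproducibility of findings can naturally mean that the HIV and age differences recur at the second visit. That needs estimates by visit.
- A mixed model is often recommended because it keeps women seen once. That advantage is unsafe here. Section 4 requires FSH and estradiol confirmation of menopause; Section 6 and Table 1 place that blood draw at Visit 2 within Aim 1, although Section 4 lists blood at both visits. On the Visit 2 schedule, a woman with Visit 1 only has no study result confirming eligibility.
- Time since HIV diagnosis, plasma viral load and ART use have no natural value in HIV-negative women, and Section 6 draws CD4 and HIV RNA only in HIV-positive women. Carrying those covariates unchanged into one model could drop the HIV-negative group.

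The Aim 2 comparison of Visits 2 and 3 is a partial answer on variability, for HIV-positive trial participants only.

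**Conclusion.** The point holds as a cheap improvement. Aim 1 plans paired swab and lavage samples for reproducibility, and Section 10 neither says how the pair is used nor plans a Visit 1 against Visit 2 analysis. For an assumed ICC of 0.4 to 0.8, complete pairs and no adjustment, using both visits lowers the detectable difference at alpha 0.05 from 0.57 to 0.47-0.54 SD for HIV. For age by HIV, with 25 per cell assumed, it falls from 1.13 to 0.95-1.07 SD. If the ICC is 0.8 to 0.9 the precision gain is small, but the reproducibility result and the advance choice of visits remain worth having.

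A reader might infer three stronger claims that the documents do not support.
- That the stated power is wrong: it reproduces.
- That both visits will be entered as independent rows. That would raise type I error for the HIV effect to about 10% to 14% at ICC 0.4 to 0.8, taking the normal approximation 2 × [1 − Φ(1.96/sqrt(1 + ICC))]. Nothing in the plan says this is intended, and the power statement counts women.
- That a large gain at alpha 0.0005 matters for testing. That level appears only in the power statement; the testing rule is raw p values and FDR, with a 0.05 FDR cutoff for secondary outcomes.

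**What to change.** Amend Section 10, Aim 1, for the swab and lavage outcomes.

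1. Analyse Visit 1 and Visit 2 values together in women whose eligibility is confirmed. Use a linear mixed model on the transformed outcome, or a generalized linear mixed model where transformation does not suffice. Include fixed effects for visit, HIV, age and age by HIV, and a random intercept per woman.
2. State how covariates that exist only in HIV-positive women are handled so that HIV-negative women stay in the model, for example by using those covariates only in an analysis within the HIV-positive group.
3. For reproducibility, report the HIV and age effects at each visit (or a visit-by-HIV term), and the Visit 1-2 ICC with 95% CI, overall and by HIV status, on the analysis scale.
4. State which sample counts as Visit 1 for a woman who is treated for infection and re-tested, and reconcile Section 4 with Section 6 and Table 1 on the visits at which blood is drawn.

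The cost is new analysis wording and slightly more analysis work. No visit or sample is added. The ICC by HIV status will be imprecise, and biopsy outcomes, taken only at Visit 2 in Aim 1, are not covered.
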